6.4.2 Objective Response Rate and Clinical Benefit Rate

Assessments of tumour response will be based on the RECIST criteria for patients with measurable disease at baseline.

ORR is defined as the proportion of responders (CR and PR). CBR is defined as the proportion of responders plus those with SD \geq 24 weeks.

Treatment comparison in ORR and CBR will be analysed using a logistic regression model with treatment factor only. Results will be expressed as the odds ratio together with the corresponding 95 % CI and p-value. The estimate of the difference in ORRs (500 mg fulvestrant – 250 mg fulvestrant) and the corresponding 2-sided 95% CI will also be presented.

The best objective response of CR, PR, SD \geq 24 weeks, SD<24 weeks or progression will be summarised.

6.4.3 Overall Survival

The formal treatment comparison for OS will be performed using a log rank test only after the proportion of reported deaths exceeds 50% of the total number of patients to be randomised across the 2 treatment groups (i.e., at least 360 deaths). Prior to that, survival will be summarised only and will not be subjected to inferential statistical analysis.

A further OS analysis will be performed when approximately 75% of randomised patients have died. The primary OS analysis will be a log rank test to estimate the hazard ratio of 500 mg fulvestrant to 250 mg fulvestrant together with the corresponding 95% CI and p-value. A secondary analysis will be the Cox proportional hazards regression model with treatment factor and the baseline covariates specified in Section 6.4.1.

OS will be summarised using the Kaplan-Meier method. Kaplan-Meier plots and Kaplan-Meier estimates of median time to death and percentage of patients alive at six-monthly intervals will be presented for each treatment group.

Further details will be provided in the Statistical Analysis Plan for the follow-up OS analysis

6.4.4 Duration of Response and Duration of Clinical Benefit

Duration of response and duration of clinical benefit will be summarised using the Kaplan-Meier method by randomised treatment. Kaplan-Meier plots and Kaplan-Meier estimates of median DoR and DoCB will be presented for each treatment.

6.4.5 Quality of life

The FACT-B quality of life instrument is to be used for this trial and the number of patients required for the analysis is based on the trial outcome index (TOI) within the FACT-B. This measure is the sum of the functional well being, physical well being and breast cancer subscale dimensions of the questionnaire.

Analyses on QoL data will be carried out using the ITT population as primary and will also be performed by study treatment actually received (i.e. patients who received at least one dose of the medication to which they were randomised) as supportive.

All FACT-B items will be scored such that a higher score represents a better QoL.

The TOI, total FACT-B and the FACT-G will be analysed longitudinally using a model with baseline covariates (as detailed in Section 6.4.1) to examine the difference in the TOI between the fulvestrant 500mg and fulvestrant 250mg groups.

The above QoL endpoints for each treatment group at each time point will be summarised using descriptive statistics and will also be presented graphically.

Also, an analysis of the time to deterioration in QOL will be carried out in the same way as the analysis of time to progression. QOL information will be collected at 4, 8, 12, 16, 20 and 24 weeks and this discrete data collection will be accounted for in the analysis by replacing the proportional hazard model with the discrete logistic model (by using the TIES = DISCRETE option in the MODEL statement of PHREG in SAS). For an individual patient a deterioration in QOL is defined as a decrease in TOI from baseline of 5 points or more. If a subject has not shown a reduction of 5 points or more at the time of analysis then the observation will be right censored using the last QOL assessment date. Covariates will be included as above.

Missing data handling for the TOI and FACT-B scales:

The reason for missing data will be identified. If data is missing at random, the technique outlined below will be used. If there is any evidence that the missing data is systematic, missing values will be handled to ensure that any possible bias is minimised. If there are

missing items, subscale scores will be prorated. The sum of the subscale is multiplied by the number of items in the subscale. This is then divided by the number of items actually answered. This is an accepted way of scoring the subscales provided that more than 50% of the questions are answered. If 50% or more of the questions are not answered, the subscale will be considered as missing. If any of the scores on the scales (PWB, FWB, BCS) comprising the TOI is missing, then the TOI score will be considered missing.

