- ^k Patients must have a bone scan within 8 weeks before treatment or a skeletal survey within 4 weeks before treatment. Any hotspots identified on the bone scan must be confirmed by X-ray, computerized tomography (CT) scan or magnetic resonance imaging (MRI), within 4 weeks prior to treatment.
- ^l All patients with metastatic bone lesions at baseline, must have bone scans or skeletal surveys every 12 weeks (± 2 weeks) until progression. Additional bone scans or skeletal surveys should be performed if clinically indicated. Abnormalities found on subsequent bone scans must also be confirmed by X-ray, CT scan, or MRI.
- ^m A tumour block (paraffin-embedded tumour tissue), if available, from either the primary tumour or a metastatic site will be sent to the central laboratory in those patients who give separate consent.
- ⁿ Quality of life will be collected at baseline and at every 4 weeks for the first 24 weeks. QoL will be collected in selected countries/centres, for approximately 100 patients.
- ^o A QoL questionnaire should also be completed at the treatment discontinuation visit if this occurs before 24 weeks.
- ^p Height is only captured at Visit 1.

Table 2 Study Plan (Survival Follow-up Phase)

Visit	Survival Follow-Up Phase
Pts receiving randomised treatment	Visits as per standard clinical practice
Serious Adverse Events ^b	X
Randomised treatment ^c	X
Survival status ^a	X
Pts who have discontinued randomised treatment	Visits as per standard clinical practice
Best response to 1 st subsequent breast cancer therapy ^d	X
Survival status ^a	X

a All patients will continue to have their survival status monitored every 12 ± 2 weeks until the final survival analysis when approximately 75% of patients have died.

b During the survival follow up phase, SAEs need only be reported for patients still receiving randomised treatment. SAEs for these patients should be collected for up to 8 weeks after the last injection of fulvestrant. SAEs to be sent directly to AZ Patient Safety.

c Fulvestrant study treatment may continue to be given/dispensed for as long as the patient receives clinical benefit. Following IDMC advice after the primary analysis, patient's treatment will be unblinded and patients who are currently receiving fulvestrant 250 mg will be given the option to transfer to fulvestrant 500 mg.

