4.3 Patient-Reported Outcomes (PROs)

The methods for collecting Patient Reported Outcomes (PRO) data are presented below.

QoL will be assessed for a sub-group of patients. This sub-group will initially include all patients in a number of selected countries. The QoL analysis will require a minimum of 100 patients and selection of participating countries will be based on availability of the translated questionnaires and suitability of investigators.

QoL will be assessed in both treatment groups using the Functional Assessment of Cancer Therapy – Breast (FACT-B) questionnaire (Appendix G).

The patient should complete a questionnaire at the scheduled clinic visit at baseline, and at each 4-weekly visit for 24 weeks or until progression, whichever occurs earlier. The patient should also complete a questionnaire at their treatment discontinuation visit if this occurs prior to 24 weeks. If any scheduled QoL assessment is not completed the reason for non-completion should be recorded.

Each centre participating with QoL assessments should allocate responsibility for QoL assessment to a specific individual (e.g., a research nurse). The AstraZeneca designee will provide training for the relevant personnel in the administration of QoL questionnaires to help avoid the key problem of missing data. Before patients are randomised, they must be informed of the rationale for the study and the study details, including the QoL questionnaire. The patients should be instructed on how to complete the questionnaire and if necessary assisted with completion of a training questionnaire that must be destroyed after completion.

It is important that the value and relevance of QoL data is explained carefully to participating patients so that they are motivated to comply with data collection. There is research evidence that patients with breast cancer value the opportunity to provide information on their QoL. The research nurse or appointed individual should also stress that the information is confidential. Therefore, if the patient has any medical problems she should discuss them with the doctor or research nurse separately from their QoL assessment.

The instructions for completion of questionnaires are:

- It must be completed before any investigations or discussions about the status of the patient's disease with the clinic staff.
- The patient must complete it herself without any intervention from family, friends, centre staff etc.

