6.4.1 Time to Progression

For the primary analysis of TTP, to assess efficacy of 500 mg fulvestrant against 250 mg fulvestrant, the following analysis will be carried out:

Formal treatment comparisons will be analysed using a log-rank test (equivalent to the Cox's proportional hazards regression model with treatment factor only) as a primary method. In addition, a secondary analysis using the Cox regression model will be performed to investigate any impact of baseline covariates. The following baseline covariates will be fitted in the Cox regression model:

- Age (≤ 65 vs >65)

- Response to last endocrine therapy received prior to fulvestrant (responsive / not responsive)
- Receptor status at diagnosis (both ER+ & PgR+ vs ER+ & PgR other)
- Visceral involvement (Yes/No)
- Last therapy received prior to fulvestrant (Aromatase Inhibitor (AI)/ Anti-Oestrogen(AO))
- Measurable disease (Yes/No)

The effects of centre and treatment by centre interaction will be investigated if possible; however, it is recognised that this investigation may be limited if recruitment at most centres is low, which will cause problems with computational convergence. No analysis will be performed for individual centres or a subgroup of centres.

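### The quality-of-life models borrow the TTP covariate list, which does not name the baseline score; depending on the response modelled, this costs precision in a subgroup of about 100 patients

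*Protocol*

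**What the plan says.** Section 6.4.5 sets the covariates of the three longitudinal models by cross-reference: "The TOI, total FACT-B and the FACT-G will be analysed longitudinally using a model with baseline covariates (as detailed in Section 6.4.1"). Section 6.4.1 introduces its list with "The following baseline covariates will be fitted in the Cox regression model" and gives six items: age group, response to the last endocrine therapy, receptor status, visceral involvement, type of last therapy, and measurable disease. For the time-to-deterioration model, 6.4.5 adds "Covariates will be included as above". In that analysis "a deterioration in QOL is defined as a decrease in TOI from baseline of 5 points or more".

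The baseline score is available. The footnotes to Table 1 in Section 3.1 say "Quality of life will be collected at baseline and at every 4 weeks for the first 24 weeks", which gives one baseline and six follow-up questionnaires.

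On size, the same footnotes say "QoL will be collected in selected countries/centres, for approximately 100 patients", while Section 4.3 says "The QoL analysis will require a minimum of 100 patients". Section 6.4.5 says that "the number of patients required for the analysis is based on the trial outcome index (TOI) within the FACT-B", but gives no difference, standard deviation or power.

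The protocol does not say whether the longitudinal response is the raw post-baseline score, the change from baseline, or all visits including baseline.

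**The concern.** A list chosen to predict progression has been reused for a questionnaire score. A patient's own starting score would ordinarily be expected to predict her later scores, and that is the one baseline variable the list lacks. An analyst who follows 6.4.5 as written fits six tumour and treatment-history factors and no baseline score.

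With 1:1 allocation there are about 50 patients per arm. Section 3.5 describes balanced blocks by centre and names no stratification by quality of life. A chance difference in baseline scores is therefore possible, and a model of post-baseline scores without the baseline carries part of it into the treatment estimate. At stake is the precision of secondary objective 7, in a comparison that is already small.

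**Working it through.** **The plan's own figure.** The 100 patients cannot be reproduced, because 6.4.5 gives no inputs. Back-solving at 50 per arm, two-sided 5% and 80% power gives a detectable standardised difference of (1.960 + 0.842) × √(2/50) = 0.56.

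**Inputs.** From the documents: six follow-up visits and about 50 per arm. Assumed: an equal correlation r between any two visits, with r = 0.5 to 0.7 as the working range; complete data; and, for the power figures only, SD 14 and a 5-point difference between arms. The 5 points are borrowed from the individual deterioration threshold.

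**Formulas.** For the mean of m follow-up visits, in units of the score variance:

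- post-baseline only: P = (1 + (m − 1)r)/m
- change from baseline: P + 1 − 2r
- adjusted for baseline: P − r²

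| | r = 0.5 | r = 0.7 |
|---|---|---|
| One visit: post-only / change / adjusted | 1.00 / 1.00 / 0.75 | 1.00 / 0.60 / 0.51 |
| Six visits: post-only / change / adjusted | 0.583 / 0.583 / 0.333 | 0.750 / 0.350 / 0.260 |
| One visit: adjusted as share of post-only | 75% | 51% |
| Six visits: adjusted as share of post-only | 57% | 35% |
| Six visits: adjusted as share of change | 57% | 74% |

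Worked case, six visits, r = 0.5: P = (1 + 2.5)/6 = 0.583; adjusted = 0.583 − 0.25 = 0.333; ratio 0.333/0.583 = 57%.

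Over a wider range, the six-visit share against post-only is 78% at r = 0.3 and 23% at r = 0.8. Against change scores it is 40% at r = 0.3 and 83% at r = 0.8.

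**Power, six-visit average.** At r = 0.5, 65% for either post-only or change rises to 87% with adjustment. At r = 0.7, 54% (post-only) or 86% (change) rises to 94%.

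**Chance imbalance.** The baseline difference between arms has standard error √(2/50) = 0.2 SD, or 2.8 points at SD 14. An imbalance of that size moves a post-only estimate by r × 2.8, which is 1.4 points at r = 0.5 and about 2.0 at r = 0.7.

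**Baseline kept as a response.** Generalised least squares with a common baseline mean in both arms gives a variance of the treatment effect, in units of the score variance, of 0.01333 at r = 0.5. The adjusted model gives 0.333 × 2/50 = 0.01333, and post-only gives 0.583 × 2/50 = 0.02333. At r = 0.7 the three values are 0.0104, 0.0104 and 0.0300. This version loses nothing.

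**Time to deterioration.** These formulas do not apply to a discrete logistic model, so no gain is quantified for it.

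**The case against.** Several points on the other side are sound.

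- **The baseline score may not be lost.** A reader might infer that the plan discards it. The text does not show that. The analysis is longitudinal, baseline is a scheduled assessment, and a model with baseline in the response vector and a common mean recovers everything. Change scores would also use baseline, though less efficiently.
- **Much of the model is left to the SAP.** Section 6.1 promises one, and 6.4.5 also omits the response, visit terms and covariance structure. Nor is the wording exclusive: where the protocol means treatment alone, as in 6.4.2, it says so. An SAP could add the baseline score without contradiction. But the protocol does choose a covariate set here, and that set does not lead an analyst to the baseline score.
- **Bias.** A reader might infer that the comparison is biased, for instance because countries were selected by availability of translations. Selection by country does not unbalance the arms. Section 4.3 initially takes all patients in the chosen countries, and allocation is randomised. Only chance imbalance remains, and an unadjusted standard error already allows for it.
- **Strongest predictor.** A reader might call the baseline score the strongest predictor available. That is plausible, but the protocol gives no correlation.
- **Time to deterioration.** Baseline already enters the event definition, so the gap is not identical. Even so, defining an event by change from baseline does not adjust for it: the chance of a 5-point fall can still depend on the starting score. Adding the covariate changes the odds ratio to one conditional on baseline, so it is not purely a gain in precision.
- **Sample size.** Section 4.3 makes 100 a minimum, so the subgroup may be larger.

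**Conclusion.** The point holds as a matter of precision. The covariates for all the quality-of-life models come from a six-item TTP list that does not name the baseline score.

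The size of the loss depends on a response variable that the protocol does not state. For the six-visit average at r = 0.5 to 0.7, adjustment leaves 57% to 35% of the variance of a post-baseline-only model and 57% to 74% of that of a change-score model. At a single visit it leaves 75% to 51% of the post-only variance. The loss is nil if baseline is a response with a common mean. The correlations and equal-correlation structure are assumptions, and complete data are assumed although scheduled questionnaires stop at progression. With fewer visits per patient, the share against post-only moves from the six-visit figure towards the single-visit one.

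This is a secondary endpoint in a subgroup. The documents support neither a claim of systematic bias nor any effect on the TTP conclusion.

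**What to change.** In Section 6.4.5:

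1. Add the baseline value of the score being analysed, as a continuous covariate, to each of the TOI, FACT-B and FACT-G longitudinal models. Alternatively, state that baseline is included as a response with a common mean across arms.
2. Add baseline TOI as a covariate in the time-to-deterioration model, and note that the odds ratio is then conditional on baseline TOI.

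The cost is a line or two of text and one degree of freedom per model, with no new data. The synopsis gives 28 February 2009 as the primary cut-off, and Section 3.1 describes that analysis as already performed. If the quality-of-life results have been analysed, report the baseline-adjusted models as labelled sensitivity analyses.

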6.4.6 Tolerability

AE and lab variables will be summarised by treatment actually received. AE data will be summarised in MedDRA by preferred term and system organ class. The number of patients who withdraw or die due to AEs will be summarised.

6.4.7 Exploratory analysis

A subgroup analysis based on ITT will be performed for patients who are both ER+ and PgR+ for the variables of TTP, ORR, OS and CBR. The same analysis as detailed in Section 6.4 will be performed on this subgroup with only treatment factor fitted to the models. No adjustment for covariates will be made.

Full details of the analyses will be provided in the Statistical Analysis Plan which will be finalised before database lock.

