3. STUDY PLAN AND PROCEDURES

3.1 Overall study design and flow chart

This Clinical Study Protocol has been subjected to a peer review according to AstraZeneca standard procedures.

This is a randomised, double-blind, parallel-group, multicentre, phase III study to compare two dose levels of fulvestrant. 720 postmenopausal women with oestrogen receptor positive advanced breast cancer who have either relapsed whilst on adjuvant endocrine therapy, or progressed whilst on first endocrine therapy for advanced disease, will be recruited.

Eligible patients will be randomised 1:1 to the following treatment groups:

- Fulvestrant 500 mg i.m. every 28 (\pm 3) days plus an additional 500 mg on day 14 (\pm 3) of first month only
- Fulvestrant 250 mg i.m. every 28 (\pm 3) days

Treatment will continue until disease progression, unless any of the criteria for treatment discontinuation are met first. If a patient progresses during the treatment period, the patient must be withdrawn from their randomised treatment and further treatment will be at the investigator's discretion.

All patients will be followed up for disease progression and survival, regardless of whether they have discontinued randomised treatment, unless they have withdrawn consent. Details of the first subsequent systemic breast cancer therapy received following discontinuation of randomised treatment (regimen and start and end date), as well as the best response to this therapy (according to the investigator's best judgment as per the RECIST criteria), will be collected.

There will be an Independent Data Monitoring Committee (IDMC) responsible for the review of safety data as detailed in Appendix D.

Following the primary analysis for TTP (and 50% survival analysis which was performed at the same time), all patients, regardless of whether they are still receiving randomised treatment, will enter the survival follow-up phase and be followed as per standard clinical practice. Patients remaining on randomised treatment will have their treatment unblinded and transferred to open label supplies. Patients who are currently receiving fulvestrant 250 mg, in consultation with their physician and the provision of re-consent to the open label follow-up phase of the study, will be given the option to be transferred to fulvestrant 500 mg.

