6.3 Description of analysis sets

The primary statistical analysis of the efficacy of 500 mg fulvestrant compared to 250 mg fulvestrant will include all randomised patients and will compare the treatment groups on the basis of randomised treatment, regardless of the treatment actually received. Therefore efficacy data will be summarised and analysed on an intention-to-treat (ITT) basis. This approach will be used when assessing time to progression, objective response rates, overall survival, clinical benefit rates, duration of clinical benefit and duration of response. Analyses on QoL data will be carried out using the ITT population as primary and will also be performed by study treatment actually received as supportive.

In addition, a per protocol (PP) analysis excluding significant protocol violators and deviators will be carried out for the primary variable of TTP using the model with treatment factor only.

A subgroup analysis based on ITT will be performed for patients who are both ER+ and PgR+ for the variables of TTP, ORR, OS and CBR.

When assessing tolerability of 500 mg fulvestrant against 250 mg fulvestrant summaries will be produced based on study treatment actually received.

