6.4 Method of statistical analysis

The hypothesis being tested in this study is:

H₀: 500 mg fulvestrant is no different than 250 mg fulvestrant

H₁: 500 mg fulvestrant is different from 250 mg fulvestrant

The hypothesis testing for treatment differences will be performed for TTP, ORR, OS and CBR. The superiority of 500 mg fulvestrant will be declared if the two-sided p-value for the treatment comparison is ≤ 0.05

No formal analysis will be performed on DoR or DoCB.

The primary analysis on the primary variable of TTP will be performed using a log-rank test (equivalent to the Cox's proportional hazards regression model with treatment factor only) in ITT population.

In addition to the log rank test for TTP (unadjusted model with treatment factor only) a Cox's regression model will also be performed with factors fitted for treatment and other baseline covariates (adjusted model).

The conclusions will be based on the unadjusted log rank test analysis as this is considered as the primary analysis. If the unadjusted analysis and the adjusted analysis yield different results, the consequence of covariate adjustment will be explored.

A secondary Per Protocol analysis of TTP will be performed using a log-rank test in order to assess the reliability of the conclusions from the primary ITT analysis.

For objective response rate and clinical benefit rate, a logistic regression model will be fitted with treatment factor only. For overall survival the log rank test will be performed (as described above for TTP). Duration of response and duration of clinical benefit will be summarised using the Kaplan-Meier method.

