6.5 Determination of sample size

The sample size calculation is based on the primary variable, TTP, and assumes exponential survival times. The sample size is driven by the number of required events. In order to detect a hazard ratio of ≤ 0.8 (or ≥ 1.25) for 500 mg fulvestrant compared to 250 mg fulvestrant, at a 2-sided significance level of 5%, with 80% power, approximately 632 events are required to have occurred in the study (i.e., 632 patients to have progressed or died)

The median time to progression for 250 mg fulvestrant in this patient population is estimated to be 5.5 months (Robertson et al 2003). A hazard ratio of 0.8 would equate to a prolongation in median TTP for 500 mg fulvestrant over 250 mg fulvestrant of 1.38 months (i.e., a median TTP of 6.88 months for 500 mg fulvestrant compared to median TTP of 5.5 months for 250 mg fulvestrant).

If 720 patients are recruited over a period of 36 months, it is anticipated that the required 632 events would be observed approximately 6 months following the end of recruitment.

The initial survival analysis will be performed after the proportion of reported deaths exceeds 50% of the total number of patients required. If 50% of deaths occur before the 632 progression events then the survival analysis will not be carried out until the 632 progression events are observed and the data is unblinded for the TTP analysis. A further overall survival analysis will be performed when approximately 75% of randomised patients have died.

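### The exploratory ER+/PgR+ subgroup analysis has no estimate for the remaining patients and no treatment-by-PgR term, so it cannot show whether the dose effect depends on PgR

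*Protocol*

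**What the plan says.** Section 6.3 (analysis sets) announces the subgroup: "A subgroup analysis based on ITT will be performed for patients who are both ER+ and PgR" positive, for TTP, ORR, OS and CBR. Section 6.4.7, headed as exploratory, repeats this and fixes the model: "The same analysis as detailed in Section 6.4 will be performed on this subgroup with only treatment factor fitted to the models". It excludes covariate adjustment and leaves full details to the SAP.

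Section 6.4, to which it refers, sets out hypothesis tests for the same four variables, with the rule "The superiority of 500 mg fulvestrant will be declared if the two-sided p-value for the treatment comparison is ≤ 0.05".

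Elsewhere in Section 6, PgR appears only as a main-effect covariate of the adjusted Cox model in Section 6.4.1, "Receptor status at diagnosis (both ER+ & PgR+ vs ER+ & PgR other". That covariate list is reused for OS (6.4.3) and quality of life (6.4.5). The only treatment interaction named is treatment by centre.

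Inclusion criterion 3 (Section 3.3.2) requires ER-positive disease in every patient. Section 4.2 asks for PgR status only where possible, so some patients may have unknown status.

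**The concern.** A test inside one subgroup asks whether there is an effect in that subgroup. It does not ask whether the effect there differs from the effect in other patients. That second question needs an estimate for the other patients and a contrast between the two. A treatment-only model fitted to PgR+ patients alone can supply neither.

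This goes beyond leaving detail to the SAP. The protocol already fixes the population, the four variables, the single-factor model and the absence of covariates. A SAP that followed Section 6.4.7 literally would inherit the limitation.

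What is at stake is interpretation. The subgroup has fewer events than the whole trial, so it can miss significance when the effect is the same in everyone. After a positive ITT result, a non-significant PgR+ result would look like loss of effect in PgR+ patients, and the protocol plans nothing that would show it to be chance.

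**Working it through.** **Inputs from the protocol.** Section 6.5 gives the target effect ("In order to detect a hazard ratio of ≤ 0.8 (or ≥ 1.25) for 500 mg fulvestrant compared to 250 mg fulvestrant"), the test level, power and events ("at a 2-sided significance level of 5%, with 80% power, approximately 632 events are required"), and what counts as an event ("632 patients to have progressed or died"). Section 3.1 gives the allocation: "Eligible patients will be randomised 1:1 to the following treatment groups".

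**Input not in the protocol.** The share *f* of TTP events in PgR+ patients. I assume 65% and show 50% to 80%.

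**Step 1. Reproduce the plan's figure.** Schoenfeld: events = 4(1.960 + 0.842)² / (ln 0.8)² = 4 × 7.849 / 0.04979 ≈ 631. Freedman's formula gives 636. Both agree with 632. With 632 events the expected Z is 0.2231 × √632 / 2 = 2.805, so power is Φ(2.805 − 1.960) = 80.1%.

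**Step 2. Power inside PgR+ when the hazard ratio is 0.80 in everyone.** Expected Z = 0.2231 × √(632*f*) / 2. At *f* = 0.65 there are 411 events, expected Z = 2.261, and power = Φ(0.301) = 62%.

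**Step 3. Discordance between ITT and PgR+.** To a normal approximation, Z(ITT) = √*f* × Z(PgR+) + √(1 − *f*) × Z(rest), with the two components independent. The correlation between Z(ITT) and Z(PgR+) is √*f*, which is 0.806 at *f* = 0.65. The bivariate normal then gives the probability that one test is significant at two-sided 5% and the other is not.

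**Step 4. Power of an interaction test.** The log ratio of the two hazard ratios has SE = √(4/d₁ + 4/d₂), where d₁ and d₂ are the events in the two groups. At *f* = 0.50, SE = √(4/316 + 4/316) = 0.159. For a ratio of 0.8, power = Φ(0.2231/0.159 − 1.960) = 29%.

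| PgR+ share of events | PgR+ events | Power in PgR+ | Power in the rest | ITT significant, PgR+ not | PgR+ significant, ITT not | Interaction power, ratio of HRs 0.8 |
|---|---|---|---|---|---|---|
| 50% | 316 | 51% | 51% | 31% | 2.1% | 29% |
| 60% | 379 | 58% | 43% | 24% | 2.2% | 28% |
| 65% | 411 | 62% | 38% | 21% | 2.3% | 27% |
| 70% | 442 | 65% | 34% | 17% | 2.3% | 25% |
| 80% | 506 | 71% | 24% | 12% | 2.3% | 20% |

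All columns except the last assume no difference by PgR. At 65%, 20.5 / 80.1 ≈ 26% of trials with a positive ITT result would show a non-significant PgR+ result by chance. With no effect in anyone, PgR+ alone is significant in 2.1% to 3.3% of trials over the same range of shares.

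The last column treats all remaining patients as PgR-. Patients with unknown status would lower it. With 632 events, the ratio of hazard ratios detectable with 80% power runs from 0.64 (*f* = 0.50) to 0.57 (*f* = 0.80). I made no calculation for OS, ORR or CBR, because the protocol gives no effect assumptions for them.

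**The case against.** The strongest reply is that the analysis is headed exploratory, that Section 6.4.7 leaves full details to the SAP, and that no objective promises to show dependence on PgR. Describing the effect in one prespecified population is legitimate. This limits the point to what the protocol fixes: the SAP may add estimates for the other patients or an interaction term. It does not remove the point, because the model that is fixed cannot answer the question that readers will put to a receptor subgroup.

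Three stronger readings are tempting, and the documents do not support them.

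- **That the subgroup inflates the trial's type I error.** Under no effect, at a 65% share, ITT or PgR+ would be significant on TTP in about 7.8% of trials. That is not the error rate of any decision in the plan. The synopsis rests the primary objective on the ITT log-rank test for TTP, and Section 6.4 bases conclusions on the unadjusted log-rank analysis.
- **That a significant PgR+ result would often rescue a negative trial.** That pattern occurs in only about 2-3% of trials, and the ITT decision rule excludes it as a basis for success.
- **That superiority will be declared in the subgroup at p ≤ 0.05.** Section 6.4.7 carries over the Section 6.4 analysis but does not restate the rule. The protocol leaves open whether the rule applies.

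It is also fair to object that an interaction test would rarely settle the matter. That stands, and it is why the fix rests on estimates and confidence intervals.

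**Conclusion.** The point holds as a limit on interpretation. As written, Sections 6.3 and 6.4.7 cannot show whether the dose effect depends on PgR, and the protocol has nothing to set a PgR+ result against. The primary conclusion is untouched.

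The size of the risk rests on a uniform hazard ratio of 0.80, 632 TTP events, a normal approximation and an assumed PgR+ share. At 65%, about one trial in five would be significant in ITT and not in PgR+ although nothing differs. Over 50-80% this runs from about 31% down to 12%. The share is not in the protocol, so the range matters more than the central figure. This is a cheap improvement worth making, not a threat to the trial's validity.

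**What to change.** In Sections 6.3 and 6.4.7, keep the PgR+ estimate but obtain it from models in all ITT patients (for ORR and CBR, those with measurable disease at baseline) with treatment, PgR status and treatment-by-PgR: Cox for TTP and OS, logistic for ORR and CBR.

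- Report the treatment effect with its 95% CI for PgR+, PgR- and PgR-unknown patients separately, because the existing category of other PgR status can mix negative with unknown.
- Base the interaction test on PgR+ versus PgR- only.
- State that these results are descriptive and that the Section 6.4 superiority rule does not apply to them.

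The cost is a change of wording and one model per endpoint, with no new data collection. The downside is low power: about 20-29% for a ratio of hazard ratios of 0.8, and less if many patients have unknown status. The text should therefore say that a non-significant interaction is not evidence of equal effects.
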